More than 60,000 infants are born between 22 to 32 weeks gestation age (very or extremely premature) annually in the US. Approximately 11% of them develop comorbidities, i.e., oral feeding difficulty, failure to thrive, delayed neurodevelopment, and maladapted parent-infant interaction. As part of the Neonatal Intensive Care Unit (NICU) hospitalization, very and extremely preterm infants inevitably endure early life toxic stress, e.g., parental separation, painful procedures, sleep fragmentation, harmful hospital organisms, and antibiotic therapy, without adequate protective buffers. Early life toxic stress results in adverse epigenetic modifications of glucocorticoid-related genes (DNA methylation of NR3C1 and HSD11B2) and dysbiosis (altered gut microbiome), both impairing neurodevelopment. These adversities further exacerbate the risk of comorbidities and inappropriate brain development during sensitive periods of neuroplasticity. Evidence suggests adverse epigenetic modifications and dysbiosis may set a life-long trajectory of risk for chronic health conditions, i.e., mental health disorders, cardiometabolic and immunologic diseases. Hence, it is a clinical and scientific priority to test an early NICU intervention to attenuate stress-related adverse epigenetic modifications and dysbiosis. Prior research has paved the way for a potential early NICU intervention as follows. Human milk influences the structure and relative abundance of healthy gut bacteria, i.e., short-chain fatty acid (SCFA)- and lactate-producing bacteria (e.g., *Bifidobacterium* and *Lactobacillus*), and neurodevelopment. Maternal nurturing, e.g., licking and grooming (in rodents), and breastfeeding and touch (in humans), promotes neurodevelopment, reduces stress, and reverses stress-related epigenetic modifications. Building on what is known, the multisensory early oral administration of human milk (M-MILK) intervention by nurses or parents is designed to provide an enjoyable and nurturing experience for infants, through a safe and consistent infant-guided provision of human milk droplets, given orally as early as 22 weeks postmenstrual age. M-MILK is implemented after every hands-on care and during the beginning of a full gavage feeding. The objective of our planned NIH R01 randomized controlled trial is to examine the efficacy of M-MILK from birth to 2 months corrected age, and the mechanisms whereby this may occur. We propose the M-MILK pilot study (N = 20): a 2-group, 10 per group, parallel design, and longitudinal randomized controlled trial in preterm infants who are born between 22 to 33 weeks gestational age. M-MILK will begin on day 3 of life. We will measure outcomes using validated methodologies: maternal postpartum depressive symptoms via the Edinburgh Postnatal Depression Scale, parent stress via the Parental Stressor Scale: NICU, parent discharge readiness via the Screening and Multi-disciplinary Risk Assessment Scale & Parent Activation Scale, neurodevelopment via the Neurobehavioral Assessment of the Preterm Infants and Ages & Stages Questionnaire-3, oral feeding skills via the Early Feeding Skills Assessment and NeoEAT, parent-infant interaction during feeding via the Nursing Child Assessment Satellite Training-Feeding Scale and Postpartum Bonding Questionnaire, DNA methylation of NR3C1 and HSD11B2 via buccal samples, and gut microbiome via fecal samples. Outcomes will be measured at baseline, 34 weeks postmenstrual age, discharge, and 2 months corrected age. The aims of this pilot study are to (1) determine the feasibility and acceptability of the M-MILK intervention by nurses and parents, (2) determine the feasibility of recruitment and retention, (3) obtain variability data for sample size estimation, and (4) evaluate the charges and costs of the NICU hospitalization and 2 months CA care between the M-MILK and control groups. M-MILK will be considered feasible if M-MILK is implemented by nurses or parents after every hands-on care and during the beginning of a full gavage feeding at least 90% of the time. The M-MILK acceptability by nurses and parents will be determined via M-MILK Acceptability Questionnaire. Recruitment and retention will be considered feasible if at least 50% of infants approached for participation enrolled, 90% of infants completed all inpatient data collection, and at least 50% of infants completed post-discharge follow-ups. This pilot study will inform our R01 application regarding the feasibility and acceptability of M-MILK and sample size estimation.

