To inform our planned R01 application, we propose the M-MILK pilot study (N = 12): a 2-group, 6 per group, parallel design, and longitudinal randomized controlled trial in infants who are born between 22 to 33 weeks gestational age. We will compare the outcomes between the M-MILK and attention control groups. M-MILK will begin on day 3 of life. We will measure outcomes using validated methodologies, e.g., maternal postpartum depressive symptoms via the Edinburgh Postnatal Depression Scale, parent stress via the Parental Stressor Scale: NICU, parent discharge readiness via the Screening and Multi-disciplinary Risk Assessment Scale & Parent Activation Scale, neurodevelopment via the Neurobehavioral Assessment of the Preterm Infants and Ages & Stages Questionnaire-3, oral feeding skills via the Early Feeding Skills Assessment and NeoEAT, parent-infant interaction during feeding via the Nursing Child Assessment Satellite Training-Feeding Scale and Postpartum Bonding Questionnaire, DNA methylation of *NR3C1* and *HSD11B2* via buccal samples, and gut microbiome via fecal samples. Outcomes will be measured at baseline, 34 weeks postmenstrual age, discharge, and 2 months corrected age. The aims of this pilot study are to (1) determine the feasibility and acceptability of the M-MILK intervention by nurses and parents, (2) determine the feasibility of recruitment and

retention, (3) obtain variability data for sample size estimation, and (4) evaluate the charges and costs of the NICU hospitalization and 2 months CA care between the M-MILK and control groups.

This innovative pilot study will be the first to examine M-MILK on a cumulative scale of clinical and molecular outcomes of infants and parents. The findings will yield novel insights regarding an early NICU intervention that is clinically safe, effective, and scalable. By promoting epigenetic protection and healthy gut microbiome, M-MILK has significant potential to improve future health outcomes and reduce the medical and financial burdens across the lifespan for very and extremely preterm infants.

IV. Study Aims

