The aims of this pilot study are to (1) determine the feasibility and acceptability of the M-MILK intervention by nurses and parents, (2) determine the feasibility of recruitment and retention, (3) obtain variability data for sample size estimation, and (4) evaluate the charges and costs of the NICU hospitalization and 2 months CA care between the M-MILK and control groups. M-MILK will be considered feasible if M-MILK is implemented by nurses or parents after every hands-on care and during the beginning of a full gavage feeding at least 90% of the time. The M-MILK acceptability by nurses and parents will be determined via M-MILK Acceptability Questionnaire. Recruitment and retention will be considered feasible if at least 50% of infants approached for participation enrolled, 90% of infants completed all inpatient data collection, and at least 50% of infants completed post-discharge follow-ups.

V. Administrative Organization

Participants will be enrolled in the Neonatal Intensive Care Unit (NICU) at Loyola University Medical Center (LUMC) (Maywood, IL). The inpatient components of the study protocol will be conducted in the NICU at LUMC. The post-discharge follow-up components of the study protocol will be conducted via phone/zoom interview. Data storage and management will be carried out via REDCap (version 10.4.0, Vanderbilt University) and a secured research network drive, hosted by the Loyola University Chicago (Maywood, IL).

Upon sample collection, buccal swab and fecal samples will be labeled only with study ID numbers and collection date, and stored in a locked cabinet in a locked laboratory at Loyola University Chicago (LUC) Center for Translational Research and Education (CTRE). All samples will be stored at room temperature. Quarterly, the buccal swab samples and fecal samples will be securely transported in a biospecimen transfer container (Saf T Pak, Austell, GA) via car to Rush University Medical Center Genomics and Microbiome Core Facility (Rush) (Chicago, IL) for processing and analyses. A Service Agreement between LUC and Rush will be submitted through LUC Research Portal.

VI. Study Design

a. Design

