The M-MILK pilot study ($N = 12$) is a 2-group, 6 per group, parallel design, and longitudinal randomized controlled trial. We will recruit preterm infants who are born between 22 to 33 weeks gestational age. We will compare the outcomes between the M-MILK and attention control groups. Infants will be enrolled into the study as soon as possible after they are admitted to the NICU. If infants are in the M-MILK group, M-MILK will begin on day 3 of life after every hands-on care and during the beginning of a full gavage feeding. We will measure outcomes using validated methodologies at baseline (enrollment), 34 weeks PMA, discharge, and 2 months CA.

b. Setting

The M-MILK pilot study will be conducted in a level III NICU at LUMC (Maywood, IL). The hospital provides care to families with diverse racial, ethnic, and socioeconomic backgrounds. The nursing staff are predominantly registered nurses and advanced nurse practitioners, and the physicians are board certified

neonatologists. Infants are fed using mother's own milk, donor milk, and/or formula. However, we will only include infants who receive mother's own milk or donor's milk.

c. Sample

We will enroll 12 preterm infants (6 per group). Anticipated a 40% attrition rate, we expect the final sample size to be 12 preterm infants. Estimates of average values and variability of continuous measures are acceptable at this sample size using the "rule of 12" as recommended.³¹

VII. Study Procedures

a. Subject Selection Procedures

i. Inclusion/Exclusion Criteria

Inclusion criteria

- Born between 22 to 33 weeks gestational age
- Mother is pumping and infant is receiving mother's own milk and/or donor's milk to be in the intervention group.

Exclusion criteria

- Congenital abnormalities in the digestive, e.g., clef lip and palate, omphalocele
- Necrotizing enterocolitis
- Congenital heart disease that requires surgery

ii. Screening procedures

After infants are admitted to the NICU, we will review their electronic medical records to screen for eligible infants according to the inclusion and exclusion criteria. Once an infant is enrolled into the study, the screening period continues until NICU discharge. The infant will be classified as screen failed and excluded if he/she develops any of the exclusion criteria.

iii. Recruitment Procedures

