Strict confidentiality of data files will be maintained. Data management will be facilitated using REDCap. SAS (v 9.4) will be used for all statistical procedures and analyses. Levels of missingness, variable distributions, and outliers will be examined throughout data collection for quality assurance as well as prior to statistical modeling. We will calculate descriptive statistics for all variables of interest to describe the variability of study variables, and conduct sample size estimation for the planned R01 application. Comparisons will be made using an intent-to-treat approach with participants analyzed in the groups to which they were randomized. Feasibility will be assessed with respect to enrollment, adherence, acceptability, and safety. We will calculate the percentage of infants who (1) were eligible, approached, consented, enrolled, and randomized over the recruitment period, (2) were retained for the duration of the study, (3) completed all inpatient data collection, and (4) completed post-discharge follow-ups. To determine the adherence of M-MILK, we will calculate the daily numbers of completed M-MILK and the daily numbers of expected M-MILK implementation (numbers of hands-on care episodes before full gavage feedings) to obtain the daily percentage of M-MILK completion. We will summarize findings from M-MILK Acceptability Questionnaire by nurses and parents. We will also summarize findings from M-MILK EPIC charting regarding infant's responses and any adverse events to monitor for the safety of M-MILK.

X. Study Timeline

Table 2. The proposed pilot study will require 1 year to complete. During the first 3 months, we will hire and train the team members. We anticipate enrolling 2 infants per month for 9 months. An additional 3 months will be required to complete the intervention and collect study data. Data entry and analyses will be ongoing. We will spend 6 months to complete data analyses. An additional 6 months will be needed to prepare the final report and disseminations.

Table 2. Study Timeline

Activity/Month	Month 1-3	Month 3-12	Month 12-15	Month 15-21	Month 21-27
Preparation & Staff Training	X				
Recruitment & Enrollment		X			
Data Collection		X	X		
Data Entry & Analyses		X	X	X	
Final Reports & Dissemination				X	X

XIII. Literature Cited

1. Barfield WD. Public Health Implications of Very Preterm Birth. *Clin Perinatol*. Sep 2018;45(3):565-577.

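### The pilot's SDs are to inform the R01 sample size with no interval or allowance for their uncertainty, which leaves the R01 N uncertain several-fold

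*Combined protocol and SAP*

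**What the plan says.** Section IV gives the third aim as "3) obtain variability data for sample size estimation". The analysis planned for that aim is one sentence in Section IX: descriptive statistics will "describe the variability of study variables, and conduct sample size estimation for the planned R01 application". Section VI.c (Sample) adds that estimates of means and variability are acceptable at this sample size under a cited rule of 12. No section mentions a confidence interval for an SD, an inflation factor, an outside SD or a sensitivity range. The R01's primary outcome, alpha, power and effect size are not given.

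The pilot's size is stated in conflicting ways:

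- Section VI.c: "We will enroll 12 preterm infants (6 per group". Section III agrees: "we propose the M-MILK pilot study (N = 12): a 2-group, 6 per group".
- The opening summary: "We propose the M-MILK pilot study (N = 20): a 2-group, 10 per group, parallel design".
- Section VI.c on losses: "Anticipated a 40% attrition rate, we expect the final sample size to be 12 preterm infants".
- Section X: 2 infants per month for 9 months, which is 18.

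The retention targets in Section IV are "90% of infants completed all inpatient data collection" and "at least 50% of infants completed post-discharge follow-ups".

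**The concern.** The required sample size for comparing two means is proportional to the variance, so an error in the SD enters the R01 N squared. An SD from a pilot this small can be far from the truth in either direction. If it is too low, the R01 is short of power; if it is too high, the R01 enrols more preterm infants than it needs. A bare SD does not show the reader how large the error could be. Supplying variability data for the R01 is one of the pilot's four aims, so the precision of those data is part of whether the aim is met.

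**Working it through.** **1. The plan's own figure.** Section VI.c expects 12 infants after 40% attrition.

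- From 12 enrolled: 12 × 0.60 = 7.2, about 7. The stated 12 is not reproduced.
- From 20 enrolled: 20 × 0.60 = 12. It is reproduced, and 20 is the size in the opening summary.
- From the 18 implied by accrual: 18 × 0.60 = 10.8. It is not reproduced.

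The sentence on attrition fits only the larger enrolment, yet the sentence before it gives the smaller one.

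**2. Degrees of freedom.** For an SD pooled within two arms, df = n − 2.

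- 12 enrolled: 10 at full sample, about 5 after attrition (7 infants).
- 20 enrolled: 18 at full sample, 10 after attrition (12 infants).
- 18 enrolled lies between these.

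If follow-up only just met the 50% target, df at 2 months would be 4 (6 of 12) or 8 (10 of 20).

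**3. Interval for the true SD.** For normal data the 95% limits are s × √(df/χ²), with χ² taken at its 97.5% and 2.5% points. The factor for N is the square of the factor for the SD.

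| df | χ² 97.5% | χ² 2.5% | True SD ÷ estimate | Factor on R01 N |
|---|---|---|---|---|
| 18 | 31.526 | 8.231 | 0.76 to 1.48 | 0.57 to 2.19 |
| 10 | 20.483 | 3.247 | 0.70 to 1.75 | 0.49 to 3.08 |
| 5 | 12.833 | 0.831 | 0.62 to 2.45 | 0.39 to 6.02 |

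**4. Consequence for R01 power.** Assumptions, none of them in the documents: two-sided alpha 0.05, an 80% power target, 1:1 allocation, and N computed from the unadjusted pooled SD s when the true SD is σ. Ignoring rounding of N,

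true power = Φ((1.960 + 0.842) × s/σ − 1.960).

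Power is below 70% when s/σ < (1.960 + 0.524)/2.802 = 0.887, that is, when s²/σ² < 0.786. Because df × s²/σ² follows a χ² distribution:

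- df 18: P(χ² < 14.155) = 28%
- df 10: P(χ² < 7.864) = 36%
- df 5: P(χ² < 3.932) = 44%

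Simulation with N rounded up, for true standardised effects of 0.3 to 0.8, gives 27 to 28%, 35 to 36% and 43 to 44%. With a 90% target, the chance that true power is below 80% is 22 to 23%, 30 to 32% and 40 to 41%.

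**5. Upper limit as a second planning value.** The one-sided 80% upper limit is s × √(df/χ²), with χ² at its 20% point (12.857, 6.179 and 2.343). The SD is multiplied by 1.18, 1.27 or 1.46, and N by 1.40, 1.62 or 2.13, at 18, 10 or 5 df.

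**The case against.** Several points on the other side have force.

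- **Use of the bare SD is not stated.** Section IX does not say that point estimates will be used unadjusted, pooled within arm, or without outside data. Outside SDs may exist for some outcomes; Table 1 describes the NAPI as having reference means and a standard deviation. This stands. Unadjusted use is an inference. It is the natural reading of descriptive statistics plus a claim of acceptability, but the power figures depend on it.
- **The plan gives a justification.** The rule of 12 is cited for exactly this purpose. It supports treating the estimates as usable for planning. It does not tell the R01 team how imprecise they are, and after attrition 12 enrolled infants become about 7.
- **The direction of error is weak evidence.** A reader might infer that an underpowered R01 is more likely than not. Under the same assumptions the pooled SD falls below the true SD with probability 54% at 18 df, 56% at 10 and 58% at 5. That is a small excess over one half, it is present to some degree at any finite df (52.7% even at 50 df), and it counts 79% power as a miss. It also depends on pooling within arm. With one overall SD that ignores arm and a true effect of 0.5 SD, the probability is 50% for 6 + 6 infants; at 0.8 SD it is 41%. Right-skewed data push the other way (64% for 6 + 6 in one lognormal case with log-SD 0.5). The documents do not support a claim about direction. The width of the interval is the point.
- **The smaller df are not certain.** A reader might take 10 df as the ceiling. The opening summary's 20 infants give 18, and the attrition sentence works only from 20. This stands, so results are given for each reading.

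**Conclusion.** The point holds as one of undisclosed imprecision. On every stated pilot size, the SDs would leave the R01 N uncertain by a wide factor: 0.57 to 2.19 at best (18 df), 0.49 to 3.08 at 10 df, and 0.39 to 6.02 if 12 enrol and 40% are lost. If the SD is used unadjusted, the chance of true power under 70% against an 80% target is about 28%, 36% and 44%.

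The intervals rest on normal data and a within-arm pooled SD. The power figures also rest on two-sided alpha 0.05, an 80% target and unadjusted use, all of which are assumptions. The documents do not show that the R01 will be underpowered. Nor do they require it to be sized on an upper limit alone; that choice trades cost against risk and belongs to the sponsor. The finding is a cheap improvement to a stated aim and does not call the pilot's design into question.

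**What to change.** 1. Reconcile the enrolled number across the opening summary, Sections III and VI, and the accrual in Section X. State enrolled and expected final numbers that agree with the 40% attrition.
2. In Section IX, report each continuous outcome's pooled within-arm SD with its df and 95% confidence interval, and say that this is the SD to be used for planning.
3. Present the R01 N at the point estimate and, beside it, at an upper confidence limit. The one-sided 80% limit is one reasonable convention (SD × 1.18, 1.27 or 1.46 at 18, 10 or 5 df). Where an outside SD is available, show the N from that too.
4. State how the final planning SD will be chosen from these.

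The cost is one chi-square limit per outcome in SAS and a few sentences of text; no pilot procedure changes. The downside is that a less favourable R01 N (× 1.40, 1.62 or 2.13) will stand beside the point-estimate N. If the R01 were sized on that limit, the chance of falling below nominal power would be 20% by construction under the same assumptions, at the price of the larger trial.

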Parents of eligible infants will be approached during their post-partum hospitalization or in the NICU at LUMC. A research team member will provide details regarding the study purpose, procedures, and answer questions. Parents will be provided with a study brochure. If parents request additional time to make their decision, we will request a phone number and ask permission to follow-up. If parents agree to have their infant participate, a written informed consent and authorization to use and disclose the PHI will be obtained. Parents will receive a copy of their signed informed consent and authorization to use and disclose the PHI. A copy of the informed consent form will be uploaded to the infant's electronic medical record. The original signed consent will be stored in a locked cabinet at LUC CTRE (Maywood, IL). Infant's participation in the study will end after the phone/Zoom interview at 2 months CA. We will provide a \$50 incentive e-gift card at NICU discharge and a \$50 incentive e-gift card at the completion of the post-discharge follow-up, a total of \$100 e-gift card. Premature infants, by virtue of their age, are unable to give consent or assent, and therefore, will not give assent or participate in the informed consent process.

iv. Randomization Procedures

Randomization is controlled by using two computer-generated lists of random numbers that are corresponded to each group: Group 1 (M-MILK) and Group 2 (attention control), balanced so that 1/2 of the infants are in each group. The lists are retained. The random numbers will be printed in order on small cards stated as Group 1 or Group 2. The cards will be placed in envelopes and placed in order in a box. Prior to approaching parents for recruitment, we will open the first envelope in the box to obtain the group assignment. We will request parents to not disclose their group assignment with other parents in the NICU. The research team

members, staff nurses, and parents cannot be blinded to the treatment condition. The research team members need to know which intervention to provide. Staff nurses provide direct care to infants. The two groups are described in the consent form as required by LUC Institutional Review Board.

v. Study Intervention

1. MMILK Intervention

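### Section X is internally inconsistent: if recruitment runs to month 12, 3 more months do not cover follow-up to 2 months corrected age for most of the eligible gestational-age range, and the accrual forecast matches neither stated sample size

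*Combined protocol and SAP*

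**What the plan says.** **Timeline (Section X and Table 2).** On accrual: "We anticipate enrolling 2 infants per month for 9 months". Table 2 places this in months 3-12. On what follows: "An additional 3 months will be required to complete the intervention and collect study data". The Data Collection row ends at month 15. Then "We will spend 6 months to complete data analyses", which matches the month 15-21 column, and a further 6 months for reporting takes the table to month 27. The same section opens with "The proposed pilot study will require 1 year to complete".

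**Entry and follow-up.** Eligible infants are born at 22 to 33 weeks (Section VII.a.i). Section VI.a says "Infants will be enrolled into the study as soon as possible after they are admitted to the NICU", and for the intervention arm "M-MILK will begin on day 3 of life after every hands-on care and during the beginning of a full gavage feeding". It also says "We will measure outcomes using validated methodologies at baseline (enrollment), 34 weeks PMA, discharge, and 2 months CA". Section VII.a.iii closes follow-up: "Infant's participation in the study will end after the phone/Zoom interview at 2 months CA".

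**Sample size.** The abstract gives N = 20. Sections III and VI.a give N = 12. Section VI.c enrols 12, anticipates 40% attrition, and expects a final sample of 12.

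**The concern.** Enrolment is planned within days of birth, and the last assessment is tied to corrected age. Time on study is therefore the time from birth to term plus 2 months, which is longest for the most immature infants. A 3-month tail after the last enrolment looks too short for that. The T4 contact carries the depression, bonding, development and feeding questionnaires and the mailed buccal and fecal kits. It also feeds the criterion for completing post-discharge follow-up and the aim on costs of care to 2 months corrected age. If the schedule is short, the 6-month final analysis is shown as starting before the last of these data exist.

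The size of the problem depends on when recruitment ends. That depends on N, on which the sections disagree.

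**Working it through.** **Inputs.** Gestational age at birth 22+0 to 33+6, the widest reading of 22 to 33 weeks (VII.a.i). Enrolment at birth, with day 3 as a variant (VI.a). Last contact at 2 months corrected age (VII.a.iii). Recruitment in months 3-12 and data collection to month 15 (Table 2). One month = 4.348 weeks. Assumption: corrected age counts from 40 weeks, with 37 weeks as a variant; the documents give no reference.

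**The plan's own figures.** The phases sum to 3 + 9 + 3 + 6 + 6 = 27 months, which agrees with Table 2 but not with a total of 1 year. The forecast is 2 × 9 = 18 infants.

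**Birth to T4** = (reference week − gestational age) / 4.348 + 2. For an infant enrolled at month 12, T4 falls at 12 plus this time, and the overrun is this time minus 3.

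| Born at | 40-week reference | T4 at month | Overrun | 37-week reference | Overrun |
|---|---|---|---|---|---|
| 22+0 | 18/4.348 + 2 = 6.14 | 18.14 | 3.14 | 15/4.348 + 2 = 5.45 | 2.45 |
| 28+0 | 12/4.348 + 2 = 4.76 | 16.76 | 1.76 | 9/4.348 + 2 = 4.07 | 1.07 |
| 33+6 | 6.143/4.348 + 2 = 3.41 | 15.41 | 0.41 | 3.143/4.348 + 2 = 2.72 | none |

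**Sensitivity.**
- Enrolment on day 3 takes off 3/30.44 = 0.10 month. Reading 2 months as 8 weeks as well, the shortest 40-week case (33+6) is 14.143/4.348 − 0.10 = 3.15 months, still above 3.
- With a 37-week reference, 3 months suffice only for births later than 37 − 4.348 = 32.65 weeks. Birth at 32+4 needs 3.02 months; birth at 32+5 needs 2.99.
- One check needs no corrected-age reference. An infant born at 22+0 and enrolled at month 12 is at 22 + 3 × 4.348 = 35.0 weeks postmenstrual age at month 15, still before term.
- The Procedures text has parents sign up for daily texts lasting as long as 20 weeks. That is 20/4.348 = 4.6 months, also more than 3.

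**Sample size and attrition.** With 40% attrition, 12 enrolled leave 12 × 0.6 = 7.2, 18 leave 10.8, and a final 12 needs 12/0.6 = 20 enrolled.

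**Effect of N at the stated 2 per month, starting at month 3 (40-week reference).**

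| N | Recruitment ends | Months left to 15 | Overrun, 33+6 to 22+0 |
|---|---|---|---|
| 12 | 3 + 6 = month 9 | 6 | none to 0.14 |
| 18 | 3 + 9 = month 12 | 3 | 0.41 to 3.14 |
| 20 | 3 + 10 = month 13 | 2 | 1.41 to 4.14 |

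**The case against.** The strongest reply is that this changes a row in a chart and nothing else. Section VII.a.iii follows each infant to T4 whatever Table 2 shows, and no rule stops data collection at month 15. Section X keeps data entry and analysis ongoing and allows 6 months for mainly descriptive statistics on a very small sample, so a delay of a few months could largely be absorbed. That stands, and it sets the weight of the point.

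The second reply is that Sections III, VI.a and VI.c plan 12 infants, and 12 at 2 per month are enrolled by month 9, when the overrun almost vanishes. The arithmetic is right, but it does not rescue Section X: the 9-month recruitment period and the recruitment row to month 12 would then be wrong. If N is 20, the overrun grows.

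The third reply is that the lower end of the range rests on a 40-week reference that the plan does not give. That also stands. At 37 weeks, births at 32+5 or later fit.

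A reader might infer that T4 data will be lost, or that the follow-up criterion is in danger. The documents do not support this: it would need a cut-off at month 15 that they do not impose. Nor can a number of affected infants be given, because the plan states no gestational-age distribution.

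**Conclusion.** Section X needs correction, as a minor planning inconsistency. If recruitment runs to month 12 and corrected age counts from 40 weeks, an infant enrolled at month 12 reaches T4 about 0.4 to 3.1 months after data collection is shown as closed. At 37 weeks the overrun is none to about 2.4 months. These are bounds for the last infant enrolled; infants enrolled earlier overrun less or not at all. Births up to about 32+4 enrolled at month 12 overrun on both references.

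The mismatch in numbers needs no assumption about corrected age. A forecast of 18 agrees with neither 12 nor 20, and enrolling 12 with 40% attrition leaves about 7, not 12.

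The practical consequence is a data-collection period shown too short and a final analysis shown as starting too early. No endpoint definition or safety rule is affected.

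**What to change.** 1. Reconcile N, attrition and accrual across the abstract and Sections III, VI.a, VI.c and X. Do this first, because it decides when recruitment ends.
2. State the reference week for corrected age.
3. Replace the fixed 3 months with a definition: data collection ends when the last enrolled infant completes the visit at 2 months corrected age.
4. Extend the Data Collection row to match. With a 40-week reference this is about month 18 if recruitment ends at month 12, about month 15 if 12 infants are enrolled by month 9, and about month 19 if 20 are enrolled by month 13. Start the final analysis after it.
5. Say which phase the 1-year statement covers, since Table 2 runs to month 27.

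Steps 2 to 5 change only wording and Table 2 and add no infants or visits. Under step 1, enrolment may have to be restated, depending on which N is intended. The downside is that the final analysis may start up to about 3 months later if recruitment ends at month 12, and hardly later at all if 12 infants are enrolled by month 9.
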